8.3.4 Additional Analyses - Subgroup

Subgroup analyses will be described for the primary outcome. We will calculate interactions between randomised groups and each subgroup variable (below). Other variables in these models will be the same as those included in the main analyses of the primary and secondary outcomes. The subgroups investigated will be: class of antidepressant medication at baseline

(SSRI, SNRI, other), baseline anxiety score (median GAD7 total score at baseline), and baseline depression score (median baseline total score PHQ9).

The principal approach we will take to analysing the withdrawal symptom phase of the study will, in principle, use the intention-to-treat principle and therefore regard the original randomised sample as the population of interest. However, we recognise that attrition could affect the interpretation of the comparison between active and placebo, especially if differential between the groups. We will therefore carry out supportive analyses to examine the likely impact of attrition including the potential use of mediation analyses and joint models.

8.3.5 Additional Analyses – Adjusted

Additional secondary analyses will adjust for the minimisation variables in addition to the treatment allocation.

8.3.6 Analysis Population and Missing Data

Outcomes will be analysed by means of Generalised Mixed Models without imputation of missing data. Measurements within individuals will be linked using a random intercept term. We will use two timepoints for the final analysis; baseline and primary timepoint at 12 weeks. An Intention-To-Treat (ITT) analysis will be carried out by randomisation group irrespective of medication compliance. The analysis population will consist of all those participants who were randomised. Mechanisms of missingness will be explored. The principal analyses will address a treatment strategy estimand, except death which will be while alive.

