5.1.2 Secondary Outcomes

Anxiety and Depression

- Anxiety scores (GAD7) at week 3, week 6, week 26 and week 30.
- Dichotomised anxiety scores (present or absent based on a cut-off of GAD7 ≥ 10) at week 3, week 6, week 12, week 26 and week 30.
- Depressive scores (PHQ9) (Gilbody *et al.*, 2007) at week 3, week 6, week 12, week 26 and week 30.
- Panic symptoms (Spitzer, 1999)

Global Improvement & Quality of Life

- EQ5D5L (Herdman *et al.*, 2011) & SF-12 (Brazier and Roberts, 2004) at week 3, week 6, week 12, week 26 and week 30

Adherence

- Adherence to study medication will be assessed using a single item asking if they are still taking study medication and a 5-item scale used in the MIR and Cobalt studies. (Wiles *et al* 2013; Kessler *et al* 2018)

Withdrawal & Adverse Events

- Adverse effects of pregabalin and antidepressants – based on the Toronto scales for antidepressants (as used in GENPOD study (Crawford *et al.*, 2014)) with additional symptoms of pregabalin side effects (including waist circumference) and pregabalin withdrawal
- Withdrawal symptoms from pregabalin – these are included in the adverse effect scale above
- Stopping the study medication

Use of alternative anxiolytic methods

- Alcohol consumption (AUDIT PC) measured at every visit (Gómez *et al.*, 2005)
- Benzodiazepine use measured at every visit

Resource Use and Employment

- Primary care resource use (6 months pre and post randomisation)
- Antidepressant medication collected from primary care medical records (6 months pre and post randomisation)
- Self-reported health resource use (baseline and 26 weeks asking about previous 6 months) including psychological therapies.
- Self-reported social care resource use (baseline and 26 weeks asking about previous 6 months)
- Employment and time off work (baseline and 26 weeks asking about previous 6 months)

Cognitive Assessments

- Exploratory Assessments of reinforcement learning, working memory and general cognitive function (administered through a web browser using the Gorilla platform)

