8.3 Statistical Considerations

8.3.1 Estimand Framework & Statistical Analysis Plan

Table 5. Estimand Framework

Characteristic of estimand	Definition and method of analysis
Population	Participants who have a diagnosis of generalised anxiety disorder, who have not responded to at least two antidepressant

	medications, who are currently still taking antidepressant medication, who are in the community, who agree to enter the trial and who do not fulfil exclusion criteria.
Treatment conditions	Pregabalin medication versus placebo in addition to care as usual
Endpoint	Natural log of the score on the Generalised Anxiety Disorder scale at 12 weeks post randomisation
Summary measure	Mean difference between natural log of the score on the Generalised Anxiety Disorder scale at 12 weeks post randomisation between those randomised to placebo versus those randomised to pregabalin (adjusting for baseline scores).
Intercurrent Events	
 i. Death before outcome While alive policy ii. Withdrawal from randomised medication (stays in trial) Treatment policy iii. Withdrawal from medication (leaves trial) While in trial policy iv. Increased use of alcohol Treatment policy v. Psychiatric admission Treatment policy vi. Commencement of psychological therapies Treatment policy

Statistical Analysis Plan

A separate Statistical Analysis Plan will be pre-specified which will be held within the Statistics Master File (SMF). It will contain following sections:

- I. Introduction
- II. Study Methods
- III. Statistical Principles
- IV. Trial Population
- V. Analysis of Primary and Secondary Outcomes (including statistical models and method of dealing with missingness)

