8.3.3 Statistical Methods – Outcomes

The primary analysis will be a generalised mixed model with identity link and Gaussian / mixed error structures, with log(e) GAD7 scores at 12 weeks as the outcome, accounting for baseline GAD7 scores using a repeated measures framework and also including minimisation factors used in the randomisation process. Natural logarithms will be used following our previous experience with the PANDA study(Lewis *et al.*, 2019) that suggested it was more efficient, and evidence that minimal clinically important differences for scales such as GAD fit a geometric model more closely. There will be two observations for each participant, the baseline and 12-week scores. These will be linked within a participant using a random intercept term. The model will be parameterised to identify baseline and post randomisation observation as one parameter, and random allocation as the second parameter. For the latter, all baseline measures will be coded as no treatment, and the post randomisation values will be classified as active or placebo. We will not make adjustments for repeated testing but will discuss the possibility that type 1 errors would have increased in the discussion.

Secondary analyses will choose the appropriate analogous generalised mixed model, for the outcome and account for the baseline measurement of the outcome. We will describe randomised groups at baseline. Summary statistics for continuous variables will be mean, median, SD, lower quartile, upper quartile and reported appropriately according to distribution. Summary statistics for binary and categorical variables will be n (%).

We will carry out supportive analyses including the minimisation variables as explanatory variables. We will also investigate baseline variables associated with missing outcome data for the primary outcome. We will carry out mediation analyses to examine the influence of missingness. All principal analyses will be complete case, intention to treat (defined as all patients randomised, analysed according to their randomised group regardless of treatment received). Although we will minimise missing data by trial conduct (building on the considerable experience and success of the team on previous studies) we will investigate the potential impact of missing data on the primary objective through threshold analyses which will impute a poor outcome for missing pregabalin patients while assuming an average outcome for missing control patients.

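### The primary model leaves out the week-3 and week-6 GAD-7, so its week-12 contrast can be biased in either direction if dropout follows early response differently in the two arms

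*Protocol*

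**What the plan says.** Section 8.3.3 describes a mixed model with a random intercept: "There will be two observations for each participant, the baseline and 12-week scores". It adds: "All principal analyses will be complete case, intention to treat". Section 8.3.6 repeats the restriction, "We will use two timepoints for the final analysis; baseline and primary timepoint at 12 weeks", and rules out filling in missing values: "Outcomes will be analysed by means of Generalised Mixed Models without imputation of missing data". Yet the same section defines the analysis population as everyone randomised.

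GAD-7 is also measured between those two points. Section 5.1.2 lists as a secondary outcome "Anxiety scores (GAD7) at week 3, week 6, week 26 and week 30", and the participant timeline in Section 5.2 confirms the visits. None of these scores enters the primary model.

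On people who leave, Table 5 in Section 8.3.1 says: "Withdrawal from medication (leaves trial) While in trial policy". Section 8.3.6 says: "The principal analyses will address a treatment strategy estimand, except death which will be while alive".

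The stated safeguards are a look at baseline predictors of missingness, mediation analyses of missingness, an exploration of missingness mechanisms, and a threshold analysis that gives missing pregabalin participants a poor outcome and missing placebo participants an average one. Section 8.1 allows for 20% attrition at 12 weeks.

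**The concern.** A participant with only a baseline score says almost nothing about the treatment difference at week 12. Whether such people are kept in the mixed model or dropped, the estimate is in effect an analysis of those seen at week 12, adjusted for baseline. That is sound if, given baseline, arm and covariates, having a week-12 score is unrelated to what that score would have been.

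Early response is an obvious reason to leave a trial, and weeks 3 and 6 record it. An active drug with common side effects and a placebo may also lose different kinds of people. The protocol recognises this for the withdrawal phase: Section 8.3.4 raises attrition that differs between groups and offers joint models. It makes no such provision for the primary outcome. At stake is a bias in the main result that scores already being collected could remove, provided missingness is at random given those scores.

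**Working it through.** **1. The plan's own figure (Section 8.1).** Effective SD: 5.6 × √(1 − 0.47²) = 4.94, stated as 4.9. Sample size per group: 2 × (1.960 + 1.282)² × 4.9² / 1.6² = 197.1, so 198 by the normal approximation and 199 with the t distribution. Total: 398 / 0.8 = 497.5, so 498. The sample size reproduces and is not in question.

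**2. Inputs for the bias check.**
- From Section 8.1: SD 5.6, baseline to week-12 correlation 0.47, effect 1.6 points, attrition up to 20%.
- Assumed, not in the protocol: correlation with week 12 of 0.6 (week 3) and 0.7 (week 6); baseline–week 3 0.60, baseline–week 6 0.55, week 3–week 6 0.70; effects of 1.0, 1.4 and 1.6 points at weeks 3, 6 and 12; normal scores on the raw scale.
- Dropout: logit of the probability of missing week 12 = intercept + slope × (week-6 score in SD units). The intercept is set separately in each arm to give the stated percentage missing.

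**3. Method.** One million simulated participants per arm. The planned estimate is week 12 regressed on baseline and arm among those observed. The comparison predicts missing week-12 scores in each arm from baseline, week 3 and week 6. The true effect is −1.60.

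| Missing | Slope (log-odds per SD) | Bias, same in both arms | Bias, one arm only | Bias, opposite directions |
|---|---|---|---|---|
| 10% | 0.35 | 0.00 | ±0.08 | ±0.17 |
| 10% | 1.0 | 0.00 | ±0.23 | ±0.47 |
| 20% | 0.35 | 0.00 | ±0.17 | ±0.35 |
| 20% | 0.7 | −0.01 | ±0.33 | ±0.66 |
| 20% | 1.0 | −0.01 | ±0.43 | ±0.88 |

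The sign depends on who leaves. At 20% and slope 0.7, if placebo non-responders leave the estimate is −1.27; if pregabalin non-responders leave it is −1.92. Using weeks 3 and 6 returned −1.59 to −1.61 throughout. If both arms share one intercept and slope, so that the better arm loses slightly fewer people, the bias is 0.04 to 0.15 for slopes of 0.7 to 1.4, with the week-3 and week-6 correlations also varied.

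**4. What attenuation does to power.** The standard error at 199 per group is 4.9 × √(2/199) = 0.491. An estimate centred on −1.27 gives Φ(1.27/0.491 − 1.96) ≈ 73%; one centred on −0.95 (opposite directions, 20%, slope 0.7) gives about 49%.

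**5. Precision if dropout is random.** Variance of week 12 given baseline: 31.36 × (1 − 0.47²) = 24.4. Given baseline, week 3 and week 6: 15.2. Share of missing information recovered: 1 − 15.2/24.4 = 0.38. With 249 per arm and 50 missing: 199 + 0.38 × 50 = 218. Power rises from 89.8% to 92.2% with SD 4.94, or from 90.3% to 92.6% with SD 4.9. For dropouts who have week 3 only, the variance is 19.5 and the recovery 1 − 19.5/24.4 = 0.20, so an effective 209 per arm and about 91%.

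**6. The estimand, side by side.** Table 5 gives people who leave the trial a while-in-trial policy. Section 8.3.6 applies treatment policy to everything except death. Both cannot hold. The two-visit model uses no post-baseline score before week 12, so it has no while-in-trial value to analyse.

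**The case against.** Nothing in the protocol says that dropout will differ by arm, and without that the bias all but vanishes. The larger figures need steep slopes in opposite directions at the full 20% allowance, whereas Section 8.1 expects much better follow-up than that. People who stop tablets are still followed up (Sections 4.2.4, 4.7 and 5.4), and a missed visit does not end contact (Section 5.5), so early non-response need not become a missing week-12 score. The early-visit correlations and slopes are assumptions, the scores are on the raw scale although the planned endpoint is log GAD-7, and letting dropout depend only on an observed week-6 score is the case that most favours the larger model. Missing data are not ignored either, and Table 5's section leaves the method of dealing with missingness partly to the SAP.

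Most of this stands, and it limits the size of the point. It does not remove it. The two-visit, complete-case model is fixed in the protocol. The only predictors of missingness it names are baseline variables, the threshold analysis tests one direction only, and no safeguard is stated to use the early scores.

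A reader might go further and infer that the result will be biased, that any bias must run against pregabalin, or that the early scores are thrown away. The documents support none of these. Bias needs an arm-specific mechanism, it can exaggerate as easily as attenuate, and weeks 3 and 6 are analysed as secondary outcomes.

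**Conclusion.** The point holds as a weakness in the primary analysis, not as a demonstrated bias. The planned model needs a stronger missing-data assumption than the collected data require. Under the assumptions listed, with 10 to 20% missing and slopes of 0.35 to 1.0, the possible bias is about 0.1 to 0.4 points if one arm is affected and 0.2 to 0.9 if the arms run in opposite directions, either way, against 1.6. That is roughly 5 to 27% and 11 to 55% of the target (0.08/1.6 to 0.43/1.6; 0.17/1.6 to 0.88/1.6). With the same mechanism in both arms it is close to zero. The gain in precision alone is modest and would not justify the change. The conflict between Table 5 and Section 8.3.6 over people who leave the trial stands whatever is assumed in the simulation.

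**What to change.** - In Sections 8.3.3 and 8.3.6, fit the primary model, on whichever outcome scale is chosen, to GAD-7 at baseline and weeks 3, 6 and 12. Include all randomised participants with any GAD-7 score, which keeps those with baseline only. Constrain the baseline mean to be equal in the two arms, as the current coding already does; add treatment-by-visit effects; and use an unstructured covariance in place of the random intercept. Keep the week-12 contrast as primary.
- Delete the complete-case wording and the restriction to two timepoints.
- Keep the threshold analysis as a sensitivity analysis, since the larger model still relies on missing at random given the observed scores.
- In Table 5, remove leaving the trial from the intercurrent events and treat it as missing data under the treatment policy, so that the table and Section 8.3.6 agree.
- Align Section 9.2, which describes the primary statistical analysis as complete case with adjustment for predictors of missingness.

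The cost is protocol and SAP wording and a slightly larger model. No new data are needed and the sample size does not change.

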8.3.7 Analysis of the Nested Qualitative study

Analysis will be conducted by members of the qualitative research team at Keele University ([name], [name] and the study researcher), with input from the Lived Experience Research Group and wider research team. The results will be presented separately from the main study results.

9 Economic Evaluations

We will estimate the incremental cost per quality adjusted life year (QALY) gained for Pregabalin, usual care and their existing antidepressant compared to their existing antidepressant and usual care only from their GP over 26 weeks from an NHS health and social care perspective for direct costs related to anxiety. QALYs will be calculated from self-reported EQ-5D-5L and the algorithm recommended by NICE (<https://www.nice.org.uk/about/what-we-do/our-programmes/nice-guidance/technology-appraisal-guidance/eq-5d-5l>). Health and social care resource will be collected from GP medical records (primary care resource use) and self-reported bespoke questionnaires (community and secondary health care resource use associated with anxiety) at baseline and 26 weeks asking about the previous 6 months. Time off work will also be collected as part of self-completed questionnaires and costed using the human capital approach and mean wage from the Office of National Statistics.

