1.2 Objectives

1. To investigate whether pregabalin, in addition to an antidepressant, is an effective and cost-effective treatment for generalised anxiety disorder (GAD) in people who have not responded to antidepressant treatment
2. To investigate any adverse effects associated with combined treatment of pregabalin and antidepressants
3. To investigate withdrawal symptoms from pregabalin when it is used in combination with antidepressants
4. To investigate the acceptability of prescribing pregabalin in addition to antidepressants for GAD from the perspectives of patients and general practitioners using qualitative methods

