Pregabalin	
1. Dizziness, somnolence, headache
	Very common ($\geq 1/10$)	The participant will be given instructions to increase the dose of the medication over the first 14 days as described in the protocol. If the participant experiences side effects, they will be advised to either remain on their current dose or reduce the dose if the side effects are not tolerable. The participant can discuss this with the PI who may also advise to stop the medication.
	
2. Nasopharyngitis
 
3. Appetite increased
 
4. Euphoric mood, confusion, irritability, disorientation, insomnia, libido decreased
 
5. Ataxia, coordination abnormal, tremor, dysarthria, amnesia, memory impairment, disturbance in attention, paraesthesia, hypoesthesia, sedation, balance disorder, lethargy
 
6. Vision blurred, diplopia
 
7. Vertigo
 
8. Vomiting, nausea, constipation, diarrhoea, flatulence, abdominal distension, dry mouth
 
9. Muscle cramp, arthralgia, back pain, pain in limb, cervical spasm
 
10. Erectile dysfunction oedema peripheral, oedema, gait abnormal,
	Common ($\geq 1/100$ to $< 1/10$)	The participant will be given instructions to increase the dose of the medication over the first 14 days as described in the protocol. If the participant experiences side effects, they will be advised to either remain on their current dose or reduce the dose if the side effects are not tolerable. The participant can discuss this with the PI who may also advise to stop the medication.

	fall, feeling drunk, feeling abnormal, fatigue 11. Weight increased		

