9.2 Within-trial analysis

Primary analysis will be within-trial intention-to-treat analysis. Outcomes will be QALYs calculated using EQ-5D-5L. Secondary analyses will include (i) using the SF-12 and the SF-6D(18) algorithm to calculate QALYs; and (ii) including the cost of absenteeism.

The cost of pregabalin will be calculated using the BNF and trial data on usage. Other antidepressant medication use collected from GP files will also be costed using the BNF.

Health care resource use will be collected from GP records and self-reported bespoke questionnaires. The design of the questionnaires will be informed by our experience in previous trials in common mental health problems. Healthcare resource use will be costed using the Personal Social Service Resource Unit (PSSRU) and NHS Reference Costs (<https://www.england.nhs.uk/national-cost-collection/>).

We will report the mean incremental cost per QALY gained of Pregabalin, usual care and their existing antidepressant compared to their existing antidepressant and usual care only from their GP over 26 weeks for all analyses. The denominator and numerator of the incremental cost per QALY gained will be calculated using regression analysis, adjusting for baseline and stratification variables in line with the statistical analysis plan. Other potential coefficients for inclusion will be considered as part of a health economics analysis plan (HEAP), signed off before database close. 95% confidence intervals, cost-effectiveness planes and cost-effectiveness acceptability curves will be calculated based on bootstrapped results and using seemingly unrelated regression to account for the correlation between costs and QALYs. We will assess patterns of missing data, with the primary analysis mirroring the primary statistical analysis (complete case analysis adjusting for predictors of missingness), with sensitivity analyses using other methods including multiple imputation using chained equations (MICE) as set out in published guidance on accounting for missing data in cost-effectiveness analyses (Sterne *et al.*, 2009). These and other sensitivity analyses accounting for any uncertainty will be detailed as part of the HEAP. Subgroup analyses for costs, EQ-5D-5L utilities and QALYs will be conducted for class of antidepressant medication at baseline, baseline anxiety score and baseline depression score.

10 Regulatory & Ethical Issues

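### Section 9 costs only anxiety-related care while QALYs count all health loss, so the cost of treating pregabalin's adverse effects may be missing from the cost per QALY

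*Protocol*

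**What the plan says.** Section 9 sets the evaluation "over 26 weeks from an NHS health and social care perspective for direct costs related to anxiety". The same paragraph divides data collection in two. Primary care use comes from GP records, with no anxiety limit stated. The rest comes from "self-reported bespoke questionnaires (community and secondary health care resource use associated with anxiety) at baseline and 26 weeks". QALYs are calculated from EQ-5D-5L.

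Other sections describe resource use without mentioning anxiety. Section 5.1.2 lists "Self-reported health resource use (baseline and 26 weeks asking about previous 6 months) including psychological therapies". Section 9.2 says "Health care resource use will be collected from GP records and self-reported bespoke questionnaires". Section 9.2 also costs pregabalin itself, names two secondary analyses (QALYs from SF-12 via SF-6D, and absenteeism), and leaves further sensitivity analyses to the HEAP. Section 9.1 requires the HEAP to be signed off before database lock.

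Table 1 in section 1.4 classes dizziness, somnolence and headache as very common with pregabalin. Its common effects include ataxia, confusion, blurred vision and "fall, feeling drunk, feeling abnormal, fatigue". Syncope and loss of consciousness are uncommon. Objective 2 in section 1.2 is "To investigate any adverse effects associated with combined treatment of pregabalin and antidepressants".

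**The concern.** A cost per QALY is interpretable when both parts describe the same consequences of treatment. Here the effect side is generic and the cost side is tied to one condition. A participant who falls on study drug and is treated in hospital loses EQ-5D-5L utility, and that loss is counted. The hospital care is not related to anxiety, so under the stated rule it is not costed. The protocol itself expects such effects.

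Objective 1 asks whether pregabalin is cost-effective. The QALY gain over 26 weeks may well be small, and dividing by a small number makes the ratio sensitive to modest costs left out of the numerator. The restriction is stated once for costing and again for the questionnaire, so it reads as a deliberate rule and not a stray phrase.

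**Working it through.** The protocol gives no cost, QALY or ratio to reproduce. The check is a comparison of text, followed by an illustration on assumed values.

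**1. What is collected and what is costed**

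| Care for an adverse effect | Collected? | Costed if section 9 is applied literally? |
|---|---|---|
| GP contact | Yes: GP records, no anxiety limit stated (sections 5.1.2 and 9) | No: not related to anxiety |
| Hospital admission | Not by the questionnaire as section 9 describes it; yes on serious adverse event forms (sections 6.1 and 6.3.2.1) | No |
| A&E without admission, outpatient or community care | Not by the questionnaire as section 9 describes it; not routinely on serious adverse event forms | No |
| Health loss from the effect | Yes: EQ-5D-5L at baseline and every follow-up | Counted in the QALYs |

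The GP and admission rows can be repaired at the analysis stage. The third row cannot, if the questionnaire really limits its items to anxiety.

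**2. Direction**

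Write ΔQ for the between-arm QALY difference (pregabalin minus placebo, taken as positive), ΔC for the cost difference under the stated rule, and ΔX for the difference in cost that the rule omits. Then

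(ΔC + ΔX)/ΔQ − ΔC/ΔQ = ΔX/ΔQ.

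The sign of the error is the sign of ΔX, which has at least two components:
- Care for adverse effects of pregabalin makes ΔX positive, so the ratio is understated.
- Section 1.1 says that reducing anxiety could also help comorbid conditions such as depression. Lower spending on that care makes ΔX negative, so the ratio is overstated.

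The documents do not say which is larger.

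**3. Illustration: ΔX/ΔQ in £ per QALY (all inputs assumed)**

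| ΔX per participant | ΔQ = 0.005 | ΔQ = 0.01 | ΔQ = 0.02 |
|---|---|---|---|
| £100 | 20,000 | 10,000 | 5,000 |
| £50 | 10,000 | 5,000 | 2,500 |
| £20 | 4,000 | 2,000 | 1,000 |
| −£20 | −4,000 | −2,000 | −1,000 |
| −£50 | −10,000 | −5,000 | −2,500 |

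For scale, at an assumed £1,000 per hospital contact, £20 to £100 per participant is an excess of 20/1,000 = 2 to 100/1,000 = 10 percentage points in the pregabalin arm. At £3,000 per contact it is 20/3,000 = 0.7 to 100/3,000 = 3.3 points.

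**The case against.** Several points on the other side are sound.

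- **Not all adverse-effect care goes unrecorded.** GP contacts are collected without an anxiety limit. Table 1 deals with very common and common effects by holding or lowering the dose, or by discussion with the investigator, and sends many of the rarer ones to the GP. The clear gap is secondary and community care, plus GP contacts that are collected but might not be costed. The questionnaire itself is not in the document, so its coverage is inferred from one parenthesis in section 9.
- **Sections 9 and 9.2 do not contradict each other.** A reader might infer a conflict because sections 5.1.2 and 9.2 do not mention anxiety. They are silent on scope, and section 9.2 sits under the section that sets the perspective. They need aligning for clarity only.
- **The restriction is even-handed in form.** It applies to both arms, and to savings as well as costs.
- **Table 1 does not give excess hospital use.** Its frequencies are not differences from placebo, and a common effect need not lead to hospital care.
- **Condition-specific costing is a recognised choice.** It reduces noise, and the HEAP can still add analyses.

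These points limit the scope, direction and size of the concern. They do not remove the mismatch. Section 9 states a rule under which a known class of drug-caused cost is excluded while its health effect is included. The HEAP can change how collected data are costed, but it cannot recover contacts that were never asked about.

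**Conclusion.** The mismatch between cost scope and QALY scope stands on the text of section 9. Followed literally, that section leaves the treatment cost of adverse effects out of the numerator, so the pregabalin arm's cost may be understated.

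A reader might go further and conclude that the cost per QALY is biased in pregabalin's favour. The protocol does not support that. Taken alone, adverse-effect care pushes that way, but omitted savings on comorbid conditions push the other way and the net sign is unknown.

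The size is also unknown. The illustrative shifts run from an understatement of £20,000 to an overstatement of £10,000 per QALY. They rest wholly on assumed costs and QALY gains, and show only that small omitted costs can matter when the 26-week gain is small.

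**What to change.** 1. In section 9 and the HEAP, define base-case costs as NHS and social care use related to anxiety or to adverse effects of study medication. Take the adverse-effect part from GP-record contacts and from admissions reported on serious adverse event forms.
2. In the HEAP, add a sensitivity analysis costing all NHS and social care use in the data collected, whatever the reason. This covers both possible directions of error.
3. State the same scope in sections 5.1.2, 9 and 9.2.
4. Check the questionnaire. If it does limit items to anxiety, widen the stem for remaining participants and report the change as a limitation.

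Items 1 to 3 need wording only and use data already collected; the HEAP is not due until database lock. Item 4 is less clean. The trial summary gives first enrolment as August 2023 and this version dates from November 2024, so earlier baselines and follow-ups would have used the old form. Serious adverse event forms do not fill that gap: they cover admissions but not ordinary A&E, outpatient or community contacts, and they have no pre-randomisation period.

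The price is a somewhat wider interval around incremental cost and some judgement in attributing contacts to adverse effects. The all-cause analysis avoids that judgement.
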